## 6. Research Plan:

The proposed study will enroll 5 NHB and 5 NHW catastrophizing participants with symptomatic knee OA. The study will over-enroll 3 additional participants due to attrition over the three-day study period. Up to 180 additional participants may undergo screening procedures and will count toward screen failures. Potential participants will undergo a standardized telephone or in-person screening which will include the pain catastrophizing questionnaire, as well as screening questions that inquire about conditions that are listed under our inclusion and exclusion criteria to confirm initial eligibility. Participants will be informed that if they do participate in this study, we will keep the information the participant provide in addition to information provided to these questions as part of this research study. If the participant does not meet inclusion criteria or decides not to participate in the study, the participant will be informed that no additional information would be collected, but any information up to that point would be maintained. Thirty potential participants will be screened to determine initial eligibility. Patients will be excluded if they have concurrent medical or arthritic conditions that could confound symptomatic knee OA related outcome measures or coexisting disease that could preclude successful completion of the protocol including: systemic rheumatic disease/condition, including rheumatoid arthritis, systemic lupus erythematosus, gout, and fibromyalgia; a history of clinically significant surgery to the index knee (e.g. open reconstruction, knee replacement or major surgery on one or both knees); uncontrolled hypertension ( $> 150/95$ ); loss of peripheral sensation in areas of the body that will be tested with QST; certain neurological diseases that could interfere with protocol completion such as s Parkinson's disease, multiple sclerosis, stroke with loss of sensory or motor function, or uncontrolled seizures; cardiovascular or peripheral arterial disease; serious psychiatric disorder requiring hospitalization within the past 12 months; diminished cognitive function that would interfere with completion of study procedures. Daily opioid use will also be an exclusion, as well as a Pain Catastrophizing Score of less than 10. Hospitalization within the preceding year for psychiatric illness, serious psychiatric disorder requiring hospitalization within the past 12 months or characterized by active suicidal ideation or diminished cognitive function that would interfere with completion of study procedures. Pregnancy will also be an exclusion. Also, contraindications to MRI scanning (e.g. presence of metal implants, claustrophobia) will be exclusion criteria. Any criteria for MRI Exclusion, such as the presence of non-removable metallic, magnetic material or devices such as pacemakers, aneurism clips, or claustrophobia, which could pose a risk for injury in the MRI scanner. The study will include questionnaires to assess pain, clinical symptoms, and pain catastrophizing. All questionnaires provided during this research study's timeline are shown in Table 2. Quantitative Sensory Testing (QST) will be performed at the Pain Clinical Research Unit (PainCRU), a fully equipped sensory testing lab within the UF Pain Research and Intervention Center of Excellence (PRICE) directed by [name] (mentor).

Brain imaging will be performed in the CTSI Human Imaging Core facility, in a 3.0 Tesla whole-body clinical MRI system (Siemens Prisma) and a 32-channel head coil will be used (see study Timeline for procedure order).

The **Pain Catastrophizing Scale (PCS)** is a reliable and valid (coefficient alpha for total PCS = 0.87), 13-item scale that assesses catastrophic thinking associated with pain [44]. We will administer the PCS using traditional instructions (a measure of trait catastrophizing) and instructions to assess State Pain Catastrophizing Scale (S-PCS) ("Thinking back to your experience during the laboratory pain testing").

**Clinical Pain.** The **Western Ontario and McMaster Universities Osteoarthritis Index (WOMAC)** [5] is a reliable (Cronbach's alpha  $\geq 0.80$ ) and well-validated measure of lower extremity pain and function in persons with OA.

The **Graded Chronic Pain Scale (GCPS)** evaluates global pain severity and pain-related interference over the past 6 months. It yields a "Characteristic Pain Intensity" and an overall "Disability" score [53]. The **Rapid Estimate of Adult Literacy in Medicine-revised (REALM-R)**. A brief test to measure the participant's ability to read common medical words, in order to determine whether the participant may need assistance with completing questionnaires.

**Quantitative Sensory Testing session (QST). Quantitative Sensory Testing Session.** Using well-established procedures from our laboratory, all participants underwent assessment of responses to pressure, and mechanical pain in a laboratory session lasting 30-60 minutes, as described previously [16; 50]. **Pressure Pain Thresholds (PPT):** was assessed at the medial and lateral joint lines of the index knee, and at the ipsilateral quadriceps, trapezius muscle and lateral epicondyle. **Punctate Mechanical Pain:** assessed at the patella of the index knee and the dorsal aspect of the ipsilateral hand using a nylon monofilament (Touchtest Sensory Evaluator 6.65) calibrated to bend at 300g of pressure. As in our previous studies [16; 50], participants were provided a pain rating following a single contact of the monofilament, after which they provided another pain rating following a series of 10 contacts at a rate of one contact per second. The difference between pain ratings for the single versus multiple contacts reflects temporal summation of mechanical pain.

**Neuroimaging Protocol.** A high-resolution, 3D structural scan will be conducted using a T1-weighted MP-RAGE sequence for use in pre-processing all functional data which will be conducted between stimulus-evoked scans (Table 1). Two **resting state scans** will be acquired using BOLD-fMRI and pCASL in order to examine functional connectivity. Participants will be asked to close their eyes during resting state scans, but to maintain alertness during the scans. Any difficulty staying awake was assessed immediately following the resting-state scan. **Stimulus-Evoked fMRI and pCASL:**

These procedure will be conducted to assess changes in regional brain activity to painful mechanical stimuli applied to the most painful knee of OA patients. Specifically, a monofilament that was individually calibrated to produce a moderate pain intensity rating of  $\leq 50$  out of 100 will be applied once per second for a total of five twenty-four second blocks to the index knee, followed by an equivalent time period of blunt stimulation (randomized order) with thirty-six second blocks

Table 2. Questionnaires administered by visit day

Day 1	Day 2	Day 3
Health History	Positive and Negative Affect Scale (PANAS)	Positive and Negative Affect Scale (PANAS)
Pain History	Western Ontario and McMaster Universities Osteoarthritis Index (WOMAC)	Treatment Expectation Questionnaire
REALM-R	Graded Chronic Pain Scale (GCPS)	Manipulation Check Questionnaire
Physical Exam Form	State Pain Catastrophizing Scale (S-PCS)	Coping Strategies Questionnaire-Revised (CSQ-R)
MRI Screening Form		State Pain Catastrophizing Scale (S-PCS)
Pain Catastrophizing Scale (PCS)		

Note: All questionnaires will be administered after written documentation of consent. S-PCS questionnaires will be administered after each pain testing task.

Table 1. MRI Sequences

Run	Paradigm	Min
-	Positioning	9.5
1	Resting fMRI BOLD Scan	8
2	Resting pCASL Scan	5
3	Mechanical Pain fMRI BOLD Scan	10
4	Anatomical Scan: T1 Weighted Image (3D)	4.5
5	Mechanical Pain pCASL Scan	10
6	Resting DWI HARDI Scan	7.5
7	FLAIR 3D (OPTIONAL Time Permitting)	5.5
		Total Time 60

of rest between each mechanical stimuli. One overall verbal pain rating (on the 0-100 scale) will be obtained following all stimuli. Data acquisition of all scans will occur in two 50.5-minutes imaging session, with 9.5 minutes for set up, resulting in a total 60-minute session.

**Randomization and General Procedures.** Individuals will be randomized to one of two groups (stratified by sex): 1) a 30-minute, single-session cognitive-behavioral intervention designed to reduce pain catastrophizing or 2) a control condition that receives pain education. Testing will occur on two days (Figure 1). On Day 1, participants will attend a laboratory session whereby informed consent will be reviewed; health, pain, and demographic history will be obtained and physical examination will be performed to identify the most symptomatic knee. Female participants of childbearing potential will complete a one-time pregnancy test at the beginning of the session on day one. Trait pain catastrophizing will be assessed prior to pain testing. Day 1 session is expected to last up to 1.5 hours. On Day 2, participants will undergo neuroimaging acquisition followed by assessment of State Pain Catastrophizing Scale (S-PCS) in response to the pain-evoked cerebral responses (see **neuroimaging protocol** above). Then, participants will complete QST assessment of responses to pressure (i.e., pressure pain threshold), and punctate mechanical stimuli (i.e., temporal summation of mechanical pain) in a laboratory session lasting 30-60 minutes. State Pain Catastrophizing Scale (S-PCS) will be assessed immediately after each pain induction procedure. There will be a 30-minute rest period between the neuroimaging and QST session. Day 2 session is expected to last 2.5 to 3 hours. On Day 3, each participant will receive either the cognitive-behavioral intervention or the pain education (control condition), followed by post-tests that will be identical to the pre-tests given on Day 2, except that participants in the pain catastrophizing reduction group will be told to use the coping strategies they learned. Once all testing is over, participants will be debriefed and provided with an honorarium. Day 3 testing session is expected to last 3 to 3.5 hours. Audio recording will be conducted at the end of the study in order to obtain feedback on what intervention techniques participants used and whether they noticed any difference during Day 3 testing. We will audio record responses to the following questions: 1) during this last testing, please tell us what you were able to do; 2) describe how you applied your techniques; 3) did you notice any difference in your reactions to the stimulations; and 4) what did you notice? Further, participants will be asked to rate on a scale from 0-10 how well they were able to use the strategies and how effective they felt the strategies were. These recording will be reviewed by the study team to assess the quality of our treatment visits. These recording will not be released and will only be accessible by study investigators. At the end of the study, the recordings will be transcribed and the audio recordings will be destroyed. State Pain Catastrophizing Scale (S-PCS) will be used as a manipulation check to verify that catastrophizing was effectively. **Pain Catastrophizing Reduction Group:** The cognitive-behavioral intervention will comprise three components: 1) general education about pain (e.g., pain pathways) and a rationale for the intervention (e.g., gate control theory); 2) impact of positive and negative pain-related thoughts on neural process of pain; and 3) a guided imaginal pain exposure exercise. We and others have successfully applied these and similar approaches to reducing pain catastrophizing [12; 13; 48; 49] (see manual for details). **Pain Education Group:** This group will receive general information about the neurobiology of pain and knee OA. At no time will they be taught about pain modulation or the interface of thoughts, feelings, and pain [48; 49].

**FMRI Analyses. Resting State BOLD:** We will perform functional connectivity analysis. Briefly, the BOLD images will be pre-processed using MATLAB Statistical Parametric Mapping software (SPM12) scripts [17]. The images will be slice time corrected, realigned, and resliced into 2mm x 2mm x 2mm voxel sized images and spatially normalized to an EPI template. Movement artifacts

[figure not shown]

Figure 1. Study Design.  
Catas=Catastrophizing; MRI=magnetic resonance imaging; QST=quantitative sensory testing.

are processed using the paradigm set forth in [7; 37]. Movement effects are first regressed from the BOLD signal. If movement is greater than 0.5mm, bad volumes will be identified and replaced with interpolated values (using nearest neighbor interpolation). Effects attributed to cerebrospinal fluid and white matter will then be regressed out from the BOLD signal. The whole data set is temporally smoothed using a band-pass butterworth filter (freq=[0.01 0.08]) and spatially smoothed using a Gaussian model (6 mm kernel), and interpolated volumes removed. Functional connectivity (r to z transformed correlations coefficients) between regions of interest (ROIs) associated with pain catastrophizing [27] (dorsolateral prefrontal cortex and anterior cingulate cortex, and insula and SI) will be assessed using the CONN Toolbox [55]. **Evoked-Pain Scans:** mechanical stimuli will be applied once per second for 10 twenty-four second periods with 36 seconds of rest periods following each stimulus series for the scan duration (as in [20]). Preprocessing steps will include: motion correction, residual motion effect removal, denoising, co-registration, spatial smoothing, and normalization. Based on the existing literature on pain-evoked stimuli, we will examine the following ROIs [4; 36]: anterior cingulate cortex, dorsolateral prefrontal cortex, and the periaqueductal gray [PAG]. These ROIs will be selected with the Wake Forest University pick atlas, which uses the Talairach Daemon database [25].

**Data Analysis.** Procedures will be put in place to ensure data integrity and the protection of subject identification. Data will be inspected for distributional form, missing values, and implausible values. We will compare data on study completers and those lost to follow-up to investigate potential biases. The assumption of normality will be checked using histograms and normal probability plots. The assumptions of regression and mediation models will be checked using residual plots and plots of influence statistics. All statistical analyses will be conducted with statistical software SAS version 9.4 (Cary, N.C.) and R version 3.2.2 (The R Foundation for Statistical Computing). All hypothesis testing conducted to address the primary aim (comparing ethnic groups on pain-related brain function, clinical pain, and pain sensitivity measures) will be two-sided with a Bonferroni corrected level of significance of .004 (.05 divided by 12 tests). Hypothesis testing using ANCOVA models will also be two-sided with a Bonferroni corrected level of significance of .004. We will control for SES and discrimination in all analyses.

We will use separate ANCOVA models to investigate the effect of the manipulation (the independent variable) on pain-related neural processes and pain measures. The measures at baseline are the covariates while the measures post-manipulation are the dependent variables. We will again use separate ANCOVA models which will include an ethnic group variable and an manipulation-ethnic group interaction term to test the hypothesis that the manipulation will produce differentiated pain-related brain responses due to ethnicity.

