## 5. Hypotheses and Specific Aims:

**Specific Aim 1:** To characterize the impact of an anti-catastrophizing manipulation on pain-related neural processes and pain among NHBs and NHWs with knee OA.

Hypothesis 1a. We hypothesize that the manipulation will produce greater reductions in experimental pain and clinical pain among NHBs than NHWs.

Hypothesis 1b. We hypothesize that the manipulation will produce greater reductions in pain-related brain responses among NHBs than NHWs.

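### The single overall pain rating after each evoked scan cannot be attributed to the painful blocks, because half of the stimulation is blunt; ask for painful and blunt ratings separately

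*Combined protocol and SAP*

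**What the plan says.** The Neuroimaging Protocol in section 6 describes a monofilament "individually calibrated to produce a moderate pain intensity rating of" at most 50 out of 100. The painful stimulus "will be applied once per second for a total of five twenty-four second blocks to the index knee". Blunt stimulation of the same total duration is given as well, the order being randomized, and rests of 36 seconds separate the stimuli. Pain during the scan is then recorded once: "One overall verbal pain rating (on the 0-100 scale) will be obtained following all stimuli".

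Under FMRI Analyses (Evoked-Pain Scans), the same task is described from the timing side: "mechanical stimuli will be applied once per second for 10 twenty-four second periods with 36 seconds of rest periods following each stimulus series". Table 1 lists two evoked runs per session, the "Mechanical Pain fMRI BOLD Scan" and a pCASL counterpart, each of 10 minutes.

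Hypothesis 1a (section 5) predicts "greater reductions in experimental pain and clinical pain among NHBs than NHWs" without itemising the measures. Data Analysis specifies separate ANCOVAs on pain measures with baseline as covariate, at a two-sided level of .004 for 12 tests. It does not list the 12 tests or mention the in-scanner rating.

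**The concern.** Participants receive two kinds of stimulation and give one number. The plan does not give the wording of the question. One participant may rate the painful filament, another the worst moment, and a third the average of the run. It is also unclear whether there is one rating per evoked run or one for both. Whichever applies, nobody can later recover how much of the number belongs to the painful blocks.

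This is the only pain-intensity report planned for the stimulation delivered in the scanner. The calibration rating comes before the run, the S-PCS measures catastrophizing, and the QST ratings come from a separate session after a 30-minute rest. The Abstract predicts reductions in both reported pain and brain activity, and presents the study as a source of preliminary data for a larger trial. An in-scanner pain change carried forward into that planning could be too small by an unknown factor. In the QST session, by contrast, the plan keeps stimulus types apart: single and repeated contacts are rated separately.

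**Working it through.** **Step 1: composition of a run.** Inputs: five painful 24 s blocks and an equivalent time of blunt stimulation (Neuroimaging Protocol); ten 24 s periods with 36 s rests (FMRI Analyses); 10 min per run (Table 1).

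- Run length: 10 × (24 + 36) s = 600 s = 10 min, which reproduces Table 1.
- Painful stimulation: 5 × 24 s = 120 s. Blunt stimulation: 120 s. Painful share: 120/240 = 50%.
- Five painful blocks alone would fill 5 × 60 s = 5 min, so the other five periods must be something else. The FMRI Analyses paragraph does not mention blunt stimulation, so five blunt blocks is an inference, but it is the reading under which both paragraphs and Table 1 agree.

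**Step 2: effect on the raw scale.** Assumed model: R = w·P + (1 − w)·B + error. P is pain from the painful blocks, B is pain from the blunt blocks, and w is the weight given to P. The effect on R is w·ΔP + (1 − w)·ΔB. Time-weighted averaging gives w = 0.5; rating only the painful stimulus gives w = 1.

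- Example with P = 50 (the calibration ceiling) and B assumed 0 to 10: at w = 0.5, R = 0.5 × 50 + 0.5 × (0 to 10) = 25 to 30.
- ΔP = 10, ΔB = 0: the effect on R is 10 at w = 1, 7.5 at w = 0.75 and 5 at w = 0.5. The loss is 0 to 50%.
- ΔB half of ΔP, w = 0.5: 0.5 × 10 + 0.5 × 5 = 7.5.
- ΔB equal to ΔP, w = 0.5: 0.5 × 10 + 0.5 × 10 = 10, no loss.

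**Step 3: effect on power.** The plan gives no SD, so these values are assumed: SD of P 20, true effect 10 on P and 0 on B. Two-sided alpha is .004 (0.05/12 = 0.00417, which the plan rounds), with 80% power and a simple comparison of two means. Per-arm n = 2 × (2.878 + 0.842)² × (SD/effect)².

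| w | SD of B | Correlation of P and B | Error SD | Raw effect | SD of R | Effect/SD | n per arm |
|---|---|---|---|---|---|---|---|
| 1 | any | any | 10 | 10 | 22.36 | 0.447 | 139 |
| 0.5 | 0 | 0 | 10 | 5 | 14.14 | 0.354 | 222 |
| 0.5 | 10 | 0.5 | 10 | 5 | 16.58 | 0.302 | 305 |
| 0.5 | 20 | 0 | 10 | 5 | 17.32 | 0.289 | 333 |
| 0.5 | 20 | 0.5 | 10 | 5 | 20.00 | 0.250 | 443 |
| 1 | 0 | 0 | 0 | 10 | 20.00 | 0.500 | 111 |
| 0.5 | 0 | 0 | 0 | 5 | 10.00 | 0.500 | 111 |

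With rating error, averaging raises the required sample by 222/139 = 1.6 to 443/139 = 3.2 times. The standardized effect falls by up to 1 − 0.250/0.447 = 44%. With constant blunt ratings and no error, the SD shrinks in step with the effect and nothing is lost.

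**Step 4: this trial.** With 10 participants and 1:1 allocation (the ratio is not stated), there are about 5 per arm. Approximate power is 2% or less in every row, including w = 1.

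**The case against.** The strongest reply is that the plan does not show any blending. The rating question is not given, and the team may intend participants to rate the painful stimulus only. That stands: dilution is a possibility with a range that includes zero. The reply does not remove the point, because a single rating of unstated scope still cannot be attributed to the painful blocks.

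Four stronger readings are tempting, and the documents do not support them:

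- **That any intervention effect is diluted.** This needs averaging, and it needs blunt ratings to respond less than painful ones. Full preservation through an equal fall in both does require blunt ratings high enough to fall that far.
- **That halving the effect requires four times the sample.** This holds only if the SD stays the same. In the cases above the SD also shrinks, and the factor is 1.6 to 3.2, or none.
- **That the rating is a trial outcome for Hypothesis 1a, or the behavioural counterpart of the brain response in 1b.** No section names it as an endpoint, and no analysis linking it to the imaging is specified. Hypothesis 1a can be tested with pressure pain thresholds and punctate ratings from QST, which are not mixed with blunt stimulation.
- **That the arms will use the scale differently.** Only the intervention arm is told to apply coping strategies at the post-test, so this is conceivable, and baseline adjustment would not remove a change arising after baseline. Nothing in the documents shows that it will happen.

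It is also fair to say that a better rating would not rescue power in a study of this size. The benefit is an interpretable estimate.

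**Conclusion.** The point holds in a limited form. The plan takes one overall rating after stimulation that is half painful and half blunt, and the result cannot be attributed to the painful blocks. If it is read as evoked pain, it may understate the raw intervention effect by 0 to 50%. The upper end assumes time-weighted averaging and no effect on blunt ratings. The loss of standardized effect runs from none to about 44% under assumed SDs, so the plan does not support any firm claim about lost power.

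The painful-versus-blunt imaging data and the QST measures do not depend on this rating. The point is still worth acting on because the missing information cannot be recovered after the scan, the remedy is almost free, and the study is meant to inform a larger one.

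**What to change.** After each evoked run (BOLD and pCASL), on both Day 2 and Day 3, ask for two 0-100 ratings: one for the painful monofilament blocks and one for the blunt blocks. Put the exact wording of both questions in the protocol, identical for both arms and both days.

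State in Data Analysis whether in-scanner pain is analysed and whether it is one of the 12 tests. If it is analysed, use the painful-block rating as the dependent variable, with its own Day 2 value as covariate, and report the blunt rating descriptively. Do not make painful minus blunt the main measure. If both ratings fall by 10 points, the difference shows 0, and it also carries the error of the blunt rating.

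The cost is one extra verbal question per run, a matter of seconds, and one more field on the form.

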**3. Abstract:**

Previous research demonstrates that non-Hispanic blacks (NHB) with osteoarthritis (OA) experience more frequent and severe clinical pain, greater disability and show a quantitative sensory testing (QST) profile suggesting impaired pain inhibition and enhanced generalized pain facilitation compared to their non-Hispanic white (NHW) counterparts. In addition, previous findings demonstrated higher pain catastrophizing (a tendency to negatively evaluate one's ability to cope with pain and to respond to anticipated or actual pain in a heightened negative cognitive and emotional manner) among NHBs compared to NHWs. While multiple factors inevitably contribute, race group differences in cognitive and affective processes (e.g. catastrophizing), represent potentially important determinants of greater clinical pain among NHBs, perhaps by altering central pain processing. Despite its pervasive negative effects, no neuroimaging study to date has experimentally manipulated pain catastrophizing and measured cerebral activity during experimentally-induced pain to determine the neural mechanisms whereby catastrophizing impacts pain responses. Moreover, the extent to which the influence of pain catastrophizing on these central pathways contributes to ethnic group differences in the experience of pain remains unexplored. To address this, the proposed study will characterize the impact of an anti-catastrophizing cognitive-behavioral intervention on pain-related neural processes and pain among NHBs and NHWs with knee OA. NHB and NHW participants with symptomatic knee OA will be randomly assigned to a brief pain catastrophizing reduction cognitive-behavioral intervention or a control group that will receive pain education. Testing will occur over three days. Participants will complete neuroimaging, including assessment of pain-evoked cerebral responses and experimental pain testing (i.e., QST) prior to and after the intervention session. Standardized quantitative sensory testing approaches will be used to assess experimental pain sensitivity, as well as their State Pain Catastrophizing Scale (S-PCS). We hypothesize that baseline levels of catastrophizing will be higher among NHB subjects and will predict increased pain sensitivity and greater pain-related brain responses among NHB participants. Moreover, we anticipate that the anti-catastrophizing reduction intervention will produce greater reductions in reported pain and in pain-related brain activity among NHB versus NHW participants. Findings from this proposed study will provide novel information regarding the neural mechanisms whereby pain catastrophizing modulates pain and the extent to which these neural processes contribute to ethnic group differences in pain responses among NHBs and NHWs with knee OA. This project will yield important preliminary data for a future grant application seeking support for a larger scale clinical intervention study targeting pain catastrophizing to reduce disparities in pain among older adults.

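### Randomization is stratified by sex but not by ethnic group, so with 5 participants per ethnic group a manipulation-by-ethnicity cell can easily hold one person

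*Combined protocol and SAP*

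**What the plan says.** Section 6, Randomization and General Procedures: "Individuals will be randomized to one of two groups (stratified by sex". Allocation ratio, block size and method are not given, and no visible text brings ethnic group into the allocation. Figure 1 (Study Design) is not available in the text reviewed.

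Section 6, opening paragraph: "The proposed study will enroll 5 NHB and 5 NHW catastrophizing participants with symptomatic knee OA". A further 3 are to be enrolled to allow for dropout, and their ethnic split is not stated.

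Section 5, Hypothesis 1a: "We hypothesize that the manipulation will produce greater reductions in experimental pain and clinical pain among NHBs than NHWs". The same prediction is made for neural responses to pain in Hypothesis 1b.

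Section 6, Data Analysis: the second set of ANCOVA models adds "an ethnic group variable and an manipulation-ethnic group interaction term". The baseline value of each measure is a covariate, and "We will control for SES and discrimination in all analyses". Tests are two-sided at .004.

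**The concern.** Both hypotheses are about a difference between two differences: the arm effect in NHB against the arm effect in NHW. Its precision depends on the smallest of four cells. The allocation protects balance on sex, which appears in no hypothesis and no stated model, and leaves balance on ethnic group to chance.

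If a group of 5 splits 4:1, one cell is one person. The interaction can still be estimated from the pooled residual variance, but that person is fitted exactly and cannot be separated from the condition. If a group splits 5:0, the interaction cannot be estimated at all.

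The Abstract says "This project will yield important preliminary data for a future grant application", so the useful output is an estimate and its precision, which is what uneven cells damage. The overall manipulation ANCOVA, without the interaction, does not need this balance and is not affected in the same way.

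**Working it through.** The plan gives no sample-size calculation or cell counts to reproduce, so the check is a direct count of how the cells can fall.

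**Inputs from the plan.** 5 NHB and 5 NHW; 3 extra for attrition; sex the only stratification factor; covariates baseline, SES and discrimination; two-sided .004.

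**Assumptions.** 1:1 allocation. Arms balanced within each sex stratum, with an odd stratum split either way with equal chance. The sex mix is unknown, so all 36 combinations of NHB women (0 to 5) and NHW women (0 to 5) are counted.

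**Worked case: 3 women and 2 men in each ethnic group.**
- Women (3 NHB, 3 NHW, 3 to each arm): the chance that k NHB women enter the intervention arm is C(3,k)² / 20, which is 0.05, 0.45, 0.45, 0.05 for k = 0 to 3.
- Men (2 NHB, 2 NHW, 2 to each arm): C(2,k)² / 6, which is 1/6, 4/6, 1/6 for k = 0 to 2.
- P(0 NHB in the intervention arm) = 0.05 × 1/6 = 0.0083.
- P(1 NHB) = 0.05 × 4/6 + 0.45 × 1/6 = 0.0333 + 0.0750 = 0.1083.
- By symmetry, P(some cell ≤ 1) = 2 × (0.0083 + 0.1083) = 0.233, and P(empty cell) = 2 × 0.0083 = 0.017.

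**Chance of a cell of 0 or 1 at 5 + 5.**

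| Allocation | Some cell ≤ 1 | Empty cell |
|---|---|---|
| 1:1 within sex, 30 of 36 sex mixes | 14.3% to 38.1% | 0% to 3.5% |
| 1:1 within sex, other 6 mixes (sex nearly coincides with ethnic group) | 0% | 0% |
| Blocks of 4 within sex, left incomplete, 3 women and 2 men per group (simulated) | about 33% | about 3.4% |
| Unrestricted coin toss | 1 − (20/32)² = 60.9% | 1 − (30/32)² = 12.1% |
| Balanced within ethnic group (3:2 in each) | 0% | 0% |

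The coin toss is shown only as an upper limit; a stratified scheme makes it unlikely.

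**Effect on precision.** Before covariate adjustment, the interaction variance is σ² × (1/n₁ + 1/n₂ + 1/n₃ + 1/n₄).
- 3:2 and 3:2: 1/3 + 1/2 + 1/3 + 1/2 = 1.667.
- One 4:1: 1/4 + 1 + 1/3 + 1/2 = 2.083, a ratio of 1.25 (SE × 1.12).
- Two 4:1: 2 × (1/4 + 1) = 2.5, a ratio of 1.50 (SE × 1.22).

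The average loss is smaller, because most draws are not 4:1. In the worked case both groups split 4:1 together, with probability 0.233 − 0.017 = 0.217. Given no empty cell, the mean variance is (0.217 × 2.5 + 0.767 × 1.667) / 0.983 = 1.85, a ratio of 1.11. Other central sex mixes give ratios up to 1.12, so SE × 1.05 to 1.06.

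**With the 3 extra participants** (split of 6 and 7 assumed).
- All 13 analysed: 0% to 12.9% for a cell of 0 or 1; 11.4% with 4 women in each group.
- 3 of the 13 lost at random, sex-only stratification: 33.9% to 55.8%, median 52.7%; empty cell 1.0% to 7.7%.
- 3 of the 13 lost at random, blocks of 2 within ethnic group (cells 3, 3, 3, 4): 33.9%; empty cell 1.0%.

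**Power.** The model has 7 parameters: intercept, arm, ethnic group, interaction, baseline, SES and discrimination, each taken as one term. With 10 participants 3 residual df remain, and the critical t at two-sided .004 is 8.05. For an interaction of 1 residual SD, power is 0.8% with 3:2 in both groups and 0.6% with 4:1 in both. For 2 residual SD it is 2.0% and 1.4%.

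**The case against.** The strongest reply is that the change makes little difference to what can be concluded. The 25% and 50% figures apply only when a bad split occurs; the average variance loss is about 11% to 12% at 5 + 5. With 13 enrolled and 3 lost at random, the median loss is about 6% in variance, or 3% in SE, and in the most favourable sex mixes it is nil. On 3 df the 95% confidence interval half-width for the interaction is about 4.1 residual SD with 3:2 in both groups (3.18 × √1.667), 4.6 with one 4:1 split and 5.0 with two. None of these is a tight estimate, and the main limit is 10 participants in a seven-parameter model. Sex is also a legitimate stratifier whether or not a hypothesis mentions it.

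All of that stands, and it sets the size of the point: a modest gain in precision. It does not remove the point. The allocation list is one of the few free protections in a study of 10, and the factor left unprotected is the one in both hypotheses. The over-enrolment is there to cover losses, so it cannot be relied on to fill cells.

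Figure 1 might show allocation within ethnic group. If it does, the text, which names sex alone, still needs to say so.

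**Conclusion.** The concern holds. On the visible text, ethnic group is not balanced across arms, although the main contrast depends on it. At 5 per group with 1:1 balance within sex, a cell of 0 or 1 has a 14% to 38% chance in most sex mixes. The risk vanishes at randomization only when sex and ethnic group nearly coincide. An empty cell is possible but rare.

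The quoted probabilities rest on the assumed ratio, balancing method, sex mix and ethnic split of the extra participants, none of which the plan states. The absence of ethnic group from the stated stratification does not rest on them. The cost is lost precision and a small risk that the interaction cannot be estimated. It should be fixed because the remedy is cheap, while recognising that the interaction test remains close to powerless either way.

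**What to change.** Make ethnic group a stratification factor, with permuted blocks of 2 or 4 within NHB and within NHW, so that each group of 5 splits 3:2 at randomization. Allocate the 3 over-enrolled participants through the same lists. State the ratio and block method, and keep the list concealed from staff who enrol.

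If sex is kept as well, use blocks of 2 in ethnicity-by-sex strata, or minimisation with ethnic group weighted first. Blocks of 4 in those strata do not solve the problem: with 3 women and 2 men per group, each group still splits 4:1 with probability 1/6, so the chance for either group is 1 − (5/6)² = 30.6%. Minimisation with a random element gives no guarantee.

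The cost is a new list before enrolment, with no extra participants, visits or procedures. The drawbacks are looser sex balance if sex is dropped and more predictable allocation with blocks of 2. Dropout can still undo the balance. In a 3:2 / 3:2 layout, 4 of the 10 participants sit in cells of 2, so a single random dropout leaves a cell of one with probability 4/10 = 40%.
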